Move better, feel better	Post-exertional malaise
	Tips for getting active
	Eating well for physical and mental health

	Managing changes to taste and smell after COVID-19
Week 7: Happiness and strengths	 Long COVID and effects on mood Happiness and hope Identifying your character strengths Understanding how using your strengths can lead to a more fulfilling life Video: The science of character strengths Managing setbacks Tips for authentic happiness; managing setbacks and keeping going
Week 8: Moving forward with Hope	 Hopes and dreams Doing something for yourself Planning pleasant activities Keeping in touch with peers Review of the programme Feedback Staying hopeful

Control group: Those allocated to the wait-list control group will access the intervention after follow-up data collection. It will be made clear to them that their responses on the measures will not be shared in an identifiable format with anyone involved in the intervention delivery and that neither their responses nor their participation in the study have any bearing on their subsequent access to the intervention.

This study will collect data from the delivery of the intervention within the community. As such, there are no criteria for discontinuing or modifying the intervention.

To improve adherence to intervention protocols, participants will receive a £10 gift voucher as thanks on completion of the questionnaires.

Owing to the setting of the study, no restrictions will be placed on the use of additional interventions or access to other care for participants.

Outcomes

Primary outcomes: Positive mental wellbeing measured using the Warwick-Edinburgh Mental Wellbeing Scale (WEMWBS) [21], at baseline and 8 weeks later. Emotional wellbeing is impacted by Long COVID [3], and our patient-public involvement groups have highlighted a desire for this to be the primary outcome measure for our self-management intervention. The measure also correlates highly with measures of mental illbeing, i.e. depression and anxiety scales [22].

Secondary outcome measures:

- 1. Self-efficacy measured by the Self-Efficacy for Managing Chronic Disease 6 item scale (SEMCD6) [23].
- 2. Fatigue measured by the Fatigue Severity Scale (FSS) [24]

- 3. Loneliness measured by the UCLA Loneliness Scale, Version 3 (UCLA3) [25]

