- 4. Depression measured by the Patient Health Questionnaire 9 item scale (PHQ9) [26]. This measure will demonstrate both potential improvements and adverse effects in relation to clinical norms.
- 5. Anxiety measured by the Generalised Anxiety Disorder 7 item scale (GAD7) [27]. This measure will demonstrate both potential improvements and adverse effects in relation to clinical norms.
- 6. Long COVID symptoms reported via the COVID-19 Yorkshire Rehabilitation Screening Tool (C19-YRS) [28].

All measured at baseline and 8 weeks later.

Mean scores will be calculated for all outcomes. Classification into "caseness" for the depression and anxiety measures will be conducted, using established norms. This will allow investigation of the proportion of people moving between caseness and non-caseness (or vice versa).

Participant timeline

Participants who have already signed-up to the Hope Programme for Long COVID will be contacted by email to invite them to take part in the study. A link will allow them to view the information sheet, email address to contact with any questions, and complete the consent form. It will be made clear that their participation in the study is an entirely voluntary additional element that will not interfere with their ability to access the intervention. If consenting, participants will receive an email link to take them to the baseline measures to complete online, one week before the intervention starts The participants will then either have access to the intervention for 8 weeks, or be placed on the waiting list. Participants living outside of CWR area knew they were on the waiting list when they completed the baseline measures. At the end of the 8 week period, all participants will be emailed a link to complete post-intervention measures - collected within the two weeks following the end of the intervention.

Sample size

This was a pragmatic trial design. Approximately 50-60 participants from CWR area who sign up for the Hope Programme intervention, being run by H4C in January 2022, will constitute the intervention group. Our experience of running digital interventions has shown that optimum group size for social interaction and peer support is approximately 50-60. Participants from outside of the CWR area will be offered a place on another Hope Programme being run in March 2022. These participants will constitute the control group

Recruitment

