Participants will be recruited via community groups and partners, social media, flyers placed in libraries, GP surgeries, long COVID clinics and through community events. Participants enrolled in the intervention will then be invited to take part in the study. This will not be a condition of their continued access to the intervention, rather explained that this is an option in addition. The delivery of this intervention in the community plans to recruit 100-120 participants.

Methods: Assignment of interventions

Allocation to the intervention or wait-list condition will be on a first-come, first-served basis. This is as our study takes place in the context of the real-life delivery of the intervention in the community. As such, there is no sequence generation. Allocation will not be concealed and no blinding will be used. All data will be collected using online questionnaires, without interaction with a researcher.

Methods: Data collection, management and analysis Data collection methods

Data will be collected at baseline and follow-up at the end of the intervention. All participants enrolled in the study will receive links to online questionnaires to complete, regardless of their engagement with the intervention platform. In addition to the measures listed as outcomes, basic demographic information will be collected (age, gender), and basic information about the impact of Long COVID on life (reduction in working hours). Long COVID symptoms will be assessed using the Covid-19 Yorkshire Rehabilitation Scale (C19-YRS) [28]. If participants do not complete their questionnaires within 7-14 days, they will be sent 3 reminders.

Data management

Data will be collected using Qualtrics, an online survey tool. No data entry will then occur by the research team, as everything will be electronically completed by participants. All completed data will be downloaded into SPSS.

Statistical methods

Descriptive statistics will summarise the characteristics of the participants and their movement through the study. Baseline characteristics and follow-up scores will be summarised.

An intention to treat analysis will take place, using multiple imputation to handle missing data.

A per-protocol (PP) analysis will also to include only those participants who completed all study questionnaires and attended at least 4 sessions of the intervention (in the intervention group), therefore are said to have "completed" the intervention.

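### The reminder rule prompts baseline questionnaires only once the course has started, no baseline cut-off is stated, and the follow-up and control-course timings are not reconciled with it

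*Protocol*

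**What the plan says.** Five statements in the protocol fix the timing.

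- **Baseline** (Participant timeline): after consent, "participants will receive an email link to take them to the baseline measures to complete online, one week before the intervention starts".
- **Follow-up** (Participant timeline): "At the end of the 8 week period, all participants will be emailed a link to complete post-intervention measures", and these are "collected within the two weeks following the end of the intervention".
- **Reminders** (Data collection methods): "If participants do not complete their questionnaires within 7-14 days, they will be sent 3 reminders". One rule covers both questionnaires. It gives no spacing and no closing date, and it does not tie baseline completion to the start of the course.
- **Control access** (Interventions, control group): "Those allocated to the wait-list control group will access the intervention after follow-up data collection". Under Sample size, the January course is the one "being run by H4C in January 2022, will constitute the intervention group", and people outside the local area are "offered a place on another Hope Programme being run in March 2022". Neither start day is given.
- **Endpoint timing** (Outcomes): the primary outcome is measured "at baseline and 8 weeks later", and the same is said of the secondary outcomes.

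Under Statistical methods, both the intention-to-treat and the per-protocol analysis compare follow-up scores between groups with the baseline score as covariate. Multiple imputation is planned for missing data in the intention-to-treat analysis.

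**The concern.** A baseline covariate has to be measured before exposure. Here the stated timings mean that anyone who needs a prompt to complete baseline is prompted when the course is already open. In the intervention arm that person may have seen week 1, which according to Table 1 covers positive emotions, gratitude and self-compassion. These topics bear directly on positive mental wellbeing, the primary outcome. A control who answers equally late has seen nothing. The distortion is therefore one-sided, and the adjustment carries it into the treatment estimate.

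Two related timings are also at stake. Follow-up reminders may fall after the two-week window has closed. A control's follow-up may also fall after the March course opens, which would break the protocol's own access rule and dilute the contrast.

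**Working it through.** The protocol gives no figure to reproduce, so the check is calendar arithmetic. Let S be the first day of the intervention course. Course end is S + 56 days and the follow-up window closes at S + 70.

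**1. Baseline reminders.** The link goes out at S - 7 and the first reminder follows 7 to 14 days later:

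- earliest: -7 + 7 = day 0
- latest: -7 + 14 = day +7

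The first reminder falls on course day 0 to +7, and the second and third cannot be earlier. No baseline reminder precedes the course. If the link went out L days ahead instead, the first reminder would fall on day 7 - L to 14 - L. It would precede the course across the whole range only if L exceeds 14; the protocol gives L = 7.

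**2. Effect on the estimate.** With baseline X, follow-up Y and common slope b, the adjusted difference is

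(mean Y, intervention - mean Y, control) - b × (mean X, intervention - mean X, control).

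If a share p of intervention-arm baselines is late and raised by d on average, mean X in that arm rises by p × d and the estimate falls by about b × p × d, treating b as unchanged. With b and d positive, this is toward zero for a beneficial course. The protocol gives none of b, p or d, so the direction is conditional and the size is not computable.

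**3. Follow-up reminders.** The link goes out on day 0 after course end, the window closes on day 14, and the first reminder is on day f = 7 to 14. With equal spacing g, the third reminder is on day f + 2g.

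| First reminder f | Spacing g | Third reminder | Inside 14 days? |
|---|---|---|---|
| 7 | 3 | 13 | yes |
| 7 | 3.5 | 14 | just |
| 7 | 7 | 21 | no |
| 14 | 1 | 16 | no |
| 14 | 7 | 28 | no |

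From day 7, all three fit if 7 + 2g ≤ 14, that is g ≤ 3.5 days. From day 14, the second and third fall outside at any spacing of a day or more.

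**4. January and March courses.** The start days are not given, so I take S from 1 to 31 January 2022.

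| S | Course end (S + 56) | Window closes (S + 70) |
|---|---|---|
| 1 January | 26 February | 12 March |
| 20 January | 17 March | 31 March |
| 31 January | 28 March | 11 April |

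Crossing 31 January dates with 31 March dates gives 961 pairs. The March course starts on or before the January course's end in 406 pairs (42%), and on or before the close of the follow-up window in 771 (80%). The remaining 190 (20%) are clean; for example, with a 3 January start the window closes on 14 March, ahead of a 21 March course. These are shares of assumed dates, not probabilities.

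**5. Interval.** With baseline completed between day -7 and day 0 and follow-up between day 56 and day 70:

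- shortest: 56 - 0 = 56 days = 8 weeks
- longest: 70 + 7 = 77 days = 11 weeks

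A baseline given on day +7 could bring the shortest interval down to 49 days, or 7 weeks.

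**The case against.** **The wording is loose.** The baseline sentence could mean a link sent on consent, for completion a week before the course. The overlap would then shrink. This is possible, but the natural reading is an email sent one week before. Neither reading supplies a cut-off.

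**Follow-up can be made to fit.** A reader might infer that all follow-up reminders come at or after the window's close. They do not: day 7 is its midpoint, and three closely spaced reminders fit. The conflict is certain only when the first comes at about day 14. What stands is that the rule permits both and the protocol does not choose.

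**Control contamination is not shown.** A reader might infer that controls gave follow-up data after starting their course. The protocol does not support this. It names months, not days, some date pairs are clean, and it states that access comes after follow-up. Where dates do overlap, 8 weeks plus the two-week window can be enough without any reminder. What stands is a calendar and a rule that must be reconciled.

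**The interval is a label.** The stated 8 weeks can be taken as shorthand for the course length, since the Participant timeline gives the actual schedule. That is fair, and the correction is one of wording. Nor is the interval necessarily 9 to 11 weeks, which would assume every baseline is completed on the day the link is sent.

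**It may be too late.** The protocol cites sources accessed in July and August 2022 and describes parts of the study in the past tense, so both courses may already have run. If so, the reminder schedule can no longer be changed, but the analysis remedy may still be open.

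**Conclusion.** The core holds on the protocol's own figures. As written, the reminder rule solicits baselines on or after the first day of the course, nothing excludes them, and they then serve as the covariate. This goes beyond a detail that could wait for an analysis plan, because the stated timings themselves produce the problem. It rests on the link being emailed at day -7.

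Bias toward zero follows only if some intervention participants answer late and week 1 has already raised their scores. A reader might want to attach a standardised size to it, but any such figure would rest on an assumed late-response rate, early gain and slope, none of which the protocol supplies.

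The follow-up limb is an unreconciled rule, certain to clash only toward the day-14 end. The March overlap is possible but depends on unstated start days. Overall severity is moderate.

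**What to change.** **If collection can still be changed**

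- Send baseline reminders within the week before the course, and close the baseline link before course access.
- Send follow-up reminders early enough for all three to fall inside the two-week window, and state a closing date.
- Close each control's follow-up link before that person gets platform access.

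**If the data are already in**

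- Use recorded completion and access dates, where they exist, to flag intervention-arm baselines given after course access and control follow-ups given after programme access.
- Treat these as missing in the planned multiple imputation, report how many there are, and add a sensitivity analysis that keeps them.
- Say how such participants are handled in the per-protocol analysis, which requires all questionnaires to be completed.

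**In either case**

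- Give the actual January and March start dates and reconcile them with the rule on control access.
- Replace the nominal 8-week interval with the actual one, about 8 to 11 weeks when baseline is completed in the week before the course.

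**Cost:** survey settings and a few lines of text, or a date check at analysis. The downside is that some late questionnaires become missing. If there are many, the loss matters in a study of 100 to 120 planned participants whose forerunner retained 60%, which is why the sensitivity analysis is needed.

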Reviewing the literature, there are very few studies reporting outcomes of interventions to support people with Long COVID. Findings are being reported from studies offering physical exercise to people at various periods following acute COVID, including those who have experienced fatigue after COVID [12]. However, these are narrow in focus and do not provide broad intervention for managing the challenges of Long COVID. A case study of the use of cognitive-behavioural therapy to specifically address anxiety and depression has been published, providing an illustration of the use of this approach [13].

There has been no research to date to evaluate the impact of Long COVID peer-support, nor to evaluate a structured peer-delivered intervention. There is ongoing research seeking to understand what techniques for self-management people with Long COVID use [14]. The challenge that these interventions potentially place some "burden" on the person to remember and direct their own care, learning and using strategies with support has been acknowledged, as particular pertinent to people with Long COVID, many of whom experience fatigue and brain fog [15]. Nevertheless, self-management interventions are recommended in various clinical guidelines [15, 16]. The only published study of outcomes of rehabilitation interventions with a self-management element we could locate reported pre-post data from an intervention ran in routine clinical practice within the National Health Service in England [17]. This seven week "course" provides management advice for various symptoms, including emotional wellbeing. Significant improvements were found in health-related quality of life. This intervention is delivered "live" online by an interdisciplinary clinical team. Digital interventions that people can use "as and when" might be particularly important for Long COVID, owing to the high levels of fatigue and "brain fog".

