Whilst there are funded studies underway to develop interventions [18], Long COVID clinics up and down the UK are faced with patients requiring support and treatment. As such, it is important to rapidly develop and evaluate interventions and support packages. There is then an outstanding need for an evidence-based, digitally delivered, peer-support self-management intervention for people living with Long COVID. Our research will evaluate a digital, peer-facilitated self-management intervention for adults with Long COVID symptoms. Our intervention has been developed from our existing self-management programme "Hope Programme for people living with cancer, in its digital format, using co-design methods with people with Long COVID [19]. We have conducted a simple

pre-post study of our intervention (in review, available in pre-print), which found a retention rate of 60% and provided initial support for the impact of the intervention through paired comparisons on positive wellbeing and self-efficacy to manage the long term condition [19]. Given the lack of established usual care or another effective intervention, there is no clear rationale for any active comparison group. Wait-list comparison was chosen for pragmatic reasons, as this study is embedded in existing planned provision of the Hope Programme

Objectives

The study seeks to test the following hypotheses: using a non-randomised wait-list control group, there will be improvements in positive mental wellbeing (primary outcome), self-efficacy, fatigue, depression, anxiety and loneliness following an 8-week digital peer-supported self-management intervention, for people living with long COVID.

Trial Design

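### With 60% retention in the team's earlier study, the protocol gives non-responders no short primary-outcome form and states no collection of reasons for stopping

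*Protocol*

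**What the plan says.** The background of the protocol describes the team's own pre-post study of this programme, "which found a retention rate of 60" per cent. The text does not define retention. The same background discusses the burden of self-management for people with Long COVID, "many of whom experience fatigue and brain fog".

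Under Outcomes, the primary measure is "Positive mental wellbeing measured using the Warwick-Edinburgh Mental Wellbeing Scale (WEMWBS) [21], at baseline and 8 weeks later". Six secondary instruments follow at the same two time points: SEMCD6, FSS, UCLA3, PHQ9, GAD7 and C19-YRS. Follow-up therefore has seven instruments, and WEMWBS has one post-baseline measurement.

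Under Data collection methods, everyone enrolled is sent the questionnaire links whether or not they use the platform. Of those who do not reply in the stated window, the protocol says "they will be sent 3 reminders". Under Interventions, a £10 voucher is given for completing the questionnaires. No shorter form, other contact route or question on reasons for stopping is described.

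Under Statistical methods: "An intention to treat analysis will take place, using multiple imputation to handle missing data". The only other analysis is per-protocol. It requires a full set of questionnaires and, in the intervention group, at least four sessions.

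On numbers, Sample size gives "Approximately 50-60 participants from CWR area who sign up for the Hope Programme intervention" and Recruitment says "The delivery of this intervention in the community plans to recruit 100-120 participants". Sample size makes no allowance for loss.

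**The concern.** The protocol gives one figure for loss in this programme, and that figure is high. It also recognises that burden matters for people with fatigue and cognitive symptoms. The follow-up procedure does not act on either point. Someone too tired for seven instruments is reminded up to three times but, as far as the protocol states, is never offered a lighter way to give the one score that the primary comparison needs.

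This matters more here than in a trial with repeated measurements. A person who misses the 8-week questionnaire contributes only a baseline WEMWBS score, with no intermediate value to inform the imputation. The per-protocol analysis drops the same people, so agreement between the two analyses would say nothing about how non-responders fared.

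The causes of loss may also differ between the groups. Only intervention participants can abandon the course before follow-up; controls receive it afterwards. Without reasons for stopping, the report could not show whether loss was related to outcome, or related in the same way in both groups.

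This is a matter of data collection. No SAP can later recover a WEMWBS score or a reason that was never requested.

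**Working it through.** The protocol has no power calculation and no dropout allowance, so there is no stated figure to reproduce. The steps below only set the scale.

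**Inputs**
- Intervention group 50 to 60, total 100 to 120 (Sample size and Recruitment). By subtraction, about 50 to 60 controls, taking equal groups as an assumption.
- Earlier retention 60% (background). Reading this as 40% missing WEMWBS at 8 weeks is an assumption.
- d = points by which non-responders truly fall below their imputed WEMWBS score. The protocol gives no basis for d; 0 to 5 is assumed.

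**Step 1: how many scores would be imputed.** In the intervention group, 0.4 × 50 = 20 to 0.4 × 60 = 24 imputed, leaving 30 to 36 observed. If the same loss held in both groups, 40 to 48 of the 100 to 120 scores would be imputed.

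**Step 2: bias in the group difference.** With missing shares m1 (intervention) and m0 (control) and shifts d1 and d0:

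bias = m1 × d1 − m0 × d0

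| m1 | m0 | Shift applies to | d = 0 | d = 3 | d = 5 |
|---|---|---|---|---|---|
| 0.4 | any | intervention only | 0 | 1.2 | 2.0 |
| 0.4 | 0.2 | both groups equally | 0 | 0.6 | 1.0 |
| 0.4 | 0.4 | both groups equally | 0 | 0 | 0 |

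Positive values favour the programme. If intervention leavers had done better than imputed, the sign reverses: d = −3 gives 0.4 × (−3) = −1.2.

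**Step 3: what recovering scores would do.** If a short form brought back WEMWBS from half of the missing intervention participants, m1 would fall from 0.4 to 0.2. The first row would become 0.2 × 3 = 0.6 and 0.2 × 5 = 1.0. This assumes that those still missing have the same d as those recovered.

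**Step 4: could a shift of this kind matter?** In SD units, take an assumed estimated effect of 0.5 SD and a baseline to follow-up correlation r of 0.5 to 0.7 (assumed). As an approximation, use SE = √(2/n) × √(1 − r²), with n the observed number per group (40% loss in both groups).
- n = 30, r = 0.5: SE = 0.224. The shift in missing intervention scores that brings the result to the edge of two-sided 5% significance is (0.5 − 1.96 × 0.224)/0.4 ≈ 0.15 SD.
- n = 36, r = 0.7: SE = 0.168. The shift is (0.5 − 1.96 × 0.168)/0.4 ≈ 0.43 SD.

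Bringing the estimate itself to zero would need 0.5/0.4 = 1.25 SD. These shifts apply to the intervention group only.

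**The case against.** Several stronger readings are tempting, and the protocol does not support them.

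- *That 40% of follow-up scores will be missing.* The 60% is undefined, may describe course retention, and comes from an uncontrolled study that says nothing about loss among controls. Here the links go out whatever the person's engagement, with reminders and a voucher. Loss could be well below 40%.
- *That the primary result rests on an untested assumption.* The imputation model and missing-data sensitivity analyses are commonly left to an SAP, which is not at hand. Their absence from the protocol is no finding.
- *That a leaver must return everything or nothing, and that each reminder repeats one request.* The protocol says nothing about forced answers, partial returns, the order of instruments or the content of the reminders. What can be said is that no shorter option is stated.
- *That the imputed analysis is a completers' analysis under another name.* People who stop the course but still answer contribute observed scores and inform the imputation.
- *That the bias favours the programme.* Equal loss with equal shift gives none, and people who leave because they have improved would reverse it. Controls are told that taking part has no bearing on later access, so they too may stop answering.

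There is also a practical objection. The protocol dates the intervention course to January 2022, yet its reference list cites material accessed in August 2022. Follow-up of that cohort may already have closed.

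These points remove any claim about the size or direction of an actual bias. They do not answer the narrower point that the protocol states no light fallback for the primary outcome and no collection of reasons for stopping.

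**Conclusion.** The point holds as a modest, inexpensive improvement to data collection. It is not an error or a contradiction in the plan. Given the only loss figure it reports and the symptoms it describes, the protocol should state a way to obtain the primary outcome from people who will not complete seven instruments, and should ask why they stopped.

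The overstatement of the group difference ranges from 0 to 2.0 WEMWBS points. That range rests on three assumptions: 40% missing in the intervention group, d between 0 and 5, and control scores imputed without error. It is 0 to 1.0 if 20% of controls are missing with the same shift, zero if loss and shift are equal, and of opposite sign if leavers did better than imputed. The significance calculation shows only that a moderate shift confined to one group could decide the result of a study this small. It does not show that such a shift is likely.

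**What to change.** In the last of the three reminders, offer both groups a short form containing WEMWBS and one tick-box item on the reason for stopping the course or the study. State in the protocol that a WEMWBS-only return counts as a primary outcome, and whether it earns the voucher.

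The cost is one extra Qualtrics link and one item. The downside is that some late responders who might have completed everything will give WEMWBS without the secondary outcomes; keeping the short form for the final reminder limits this.

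If follow-up of the January 2022 cohort has closed, the change can apply only to later cohorts. For this one, the report should give the number of missing WEMWBS scores by group and say that the protocol provided for no collection of reasons.
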